## 5.7. Dose Modifications

Each dose modification or treatment delay must be documented, including the respective reason. The reason for dose modification should be directly related to a selinexor-associated AE, and not due to disease symptom/sign or to other medications.

For all Grade  $\geq 3$  hematological or non-hematological AEs that are NOT selinexor related, after consultation with the Medical Monitor and at the discretion of the Investigator, selinexor dosing may be maintained.

Selinexor should be discontinued for all selinexor-related life-threatening (Grade 4) AEs.

[Table 4](#) summarizes the selinexor dose levels; [Table 5](#) describes supportive care and dose adjustment guidelines. Deviations from the guidelines are permitted after discussion between the Sponsor and the treating physician.

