| Life-threatening consequences  | Any        | 
 
• Interrupt selinexor and administer appropriate care with blood transfusions and/or other treatments per clinical guidelines.
 
• Monitor until patient stabilizes and hemoglobin is >8.0 g/dL.
 
• Restart selinexor at 1 dose level lower (see Table 4).
 
 |
| Non-Hematologic Adverse Reactions   |            |  |
| Hyponatremia  |            |  |
| Sodium level 130 mmol/L or less not due to disease or fluid status               | Any        | 
 
• Interrupt selinexor and provide appropriate supportive care.
 
• Monitor until sodium levels return to 130 mmol/L or higher.
 
  |

| Adverse Reaction a   | Occurrence                     | Action   |
|---|--------------------------------|--|
| 
 
Restart selinexor at 1 dose level lower (see Table 4).
 
  |                                |  |
| Nausea and Vomiting  |                                |  |
| Grade 1 or 2 nausea (oral intake decreased without significant weight loss, dehydration or malnutrition)
OR Grade 1 or 2 vomiting (5 or fewer episodes per day) | Any                            | 
 
Maintain selinexor and initiate additional anti-nausea medications.
 
  |
| Grade 3 nausea (inadequate oral caloric or fluid intake)
OR Grade 3 or higher vomiting (6 or more episodes per day)   | Any                            | 
 
Interrupt selinexor.
 
Monitor until nausea or vomiting has resolved to Grade 2 or lower or baseline.
 
Initiate additional anti-nausea medications for Grade 2 or lower.
 
Restart selinexor at 1 dose level lower (see Table 4)
 
 |
| Diarrhea   |                                |  |
| Grade 2 (increase of 4 to 6 stools per day over baseline)   | 1 st                | 
 
Maintain selinexor and institute supportive care.
 
  |
|   | 2 nd and subsequent | 
 
Reduce selinexor by 1 dose level (see Table 4).
 
Institute supportive care.
 
  |

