| Grade 3 or higher (increase of 7 stools or more per day over baseline; hospitalization indicated)   | Any                            | 
 
Interrupt selinexor and institute supportive care.
 
Monitor until diarrhea resolves to Grade 2 or lower.
 
Restart selinexor at 1 dose level lower (see Table 4).
 
   |
| Weight Loss and Anorexia   |                                |  |
| Weight loss of 10% to less than 20%
OR anorexia associated with significant weight loss or malnutrition not due to intensive care status                        | Any                            | 
 
Interrupt selinexor and institute supportive care.
 
Monitor until weight returns to more than 90% of baseline weight.
 
Restart selinexor at 1 dose level lower (see Table 4).
 
  |
| Other Adverse Reactions  |                                |  |
| Grade 3 or 4 non-hematologic reactions  | Any                            | 
 
Interrupt selinexor.
 
Monitor until resolved to Grade 2 or lower, restart selinexor at 1 dose level lower (see Table 4).
 
   |
| Life-threatening hematological and non-hematological (Grade 4) AEs related to selinexor  | Any                            | 
 
Discontinue selinexor
 
  |

a National Cancer Institute Common Terminology Criteria for Adverse Events (NCI CTCAE) version 5.0. Only adverse reactions to selinexor should lead to dose adjustments.

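### Two rows of protocol Table 5 direct a selinexor restart after Grade 4 or life-threatening reactions that the rest of the protocol treats as grounds for stopping

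*Protocol*

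**What the plan says.** **Restart rows.** Under Other Adverse Reactions, Table 5 has a row for "Grade 3 or 4 non-hematologic reactions". Its action is to interrupt and then: "Monitor until resolved to Grade 2 or lower, restart selinexor at 1 dose level lower". Under Anemia, the row for "Life-threatening consequences" directs interruption, transfusion or other care, monitoring until the patient is stable with hemoglobin above 8.0 g/dL, and a restart one dose level lower.

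**Rows that reach Grade 4 only by an open upper end.** The vomiting row is labelled "Grade 3 or higher vomiting (6 or more episodes per day" and the diarrhea row "Grade 3 or higher (increase of 7 stools or more per day over baseline; hospitalization indicated". Both also lead to a restart one level lower.

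**Stop rule.** The last row of Table 5 covers "Life-threatening hematological and non-hematological (Grade 4) AEs" related to selinexor, and its action is discontinuation. Four other places say the same for related Grade 4 events: the text of Section 5.7, Section 6.1, the list in Section 6.2 of reasons for which the investigator *must* remove a patient from treatment, and the synopsis list (Duration of Treatment and Follow-up) of events on which therapy *will* be stopped.

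**Scope of the table.** Footnote a to Table 5 says: "Only adverse reactions to selinexor should lead to dose adjustments". Section 5.7 says: "The reason for dose modification should be directly related to a selinexor-associated AE".

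**The concern.** For one and the same event, a selinexor-related Grade 4 non-hematologic reaction, two neighbouring rows of Table 5 give opposite instructions. The same holds for life-threatening anemia, where the specific row and the last row disagree.

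Table 5 is the event-by-event dosing guide. A clinician who looks up the event finds a specific row that directs a restart. Following it would breach Section 6.2 and re-expose a patient after a related life-threatening reaction. Two sites could also treat identical patients differently, each citing the protocol. What is at stake is patient safety and consistent conduct, not the analysis.

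**Working it through.** The plan gives no figure to reproduce. The check compares texts and then counts doses.

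**Step 1. Do the restart rows concern related events?** Footnote a and Section 5.7 limit dose adjustments to reactions attributed to selinexor. Section 5.7 handles unrelated events of Grade 3 or above separately: dosing may be maintained after consulting the Medical Monitor. The restart rows are therefore most naturally read as covering related reactions, as the last row does.

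**Step 2. Do they reach Grade 4?** The general non-hematologic row names Grade 4. The anemia row says life-threatening, and Sections 5.7 and 6.1 use life-threatening and Grade 4 as the same thing. So does the fallback severity scale in Section 8.1.2.2.

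**Step 3. The instructions side by side.**

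| Related event | Specific row of Table 5 | Last row, 5.7, 6.1, 6.2, synopsis |
|---|---|---|
| Grade 4 non-hematologic | Interrupt, restart one level lower | Discontinue |
| Life-threatening anemia | Interrupt, restart one level lower | Discontinue |
| Grade 4 vomiting or diarrhea (only through the open upper end) | Interrupt, restart one level lower | Discontinue |

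The first two lines are explicit conflicts. The third is secondary. Vomiting of Grade 3 or above also has its own mandatory stop in Section 6.2 when it persists despite optimal antiemetics.

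**Step 4. Does any text settle it?** No sentence says which row governs. If the last row is assumed to override silently, the 4 in the general row's label and the whole life-threatening anemia row have no use.

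**Step 5. How many doses could follow by Day 14?** The reduced level in Table 4 is Days 1 and 3 of each week, so the reduced-level dosing days up to Day 14 are {1, 3, 8, 10}. The ceiling is the number of those days later than the last dose before the event, with recovery assumed immediate.

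| Event follows the dose on | Dosing days left by Day 14 | Ceiling |
|---|---|---|
| Day 1 | 3, 8, 10 | 3 |
| Day 3 | 8, 10 | 2 |
| Day 5 | 8, 10 | 2 |
| Day 8 | 10 | 1 |
| Day 10 | none | 0 |
| Day 12 | none | 0 |

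Reaching 3 requires a life-threatening event after Day 1 to resolve to Grade 2 or lower before Day 3 (for anemia, to be stable with hemoglobin above 8.0 g/dL). Any real interruption lowers the count.

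**Step 6. Days 15 to 28.** The synopsis (Overall Study Design) and Section 3.1 make continued dosing conditional on the patient meeting none of the stopping criteria. The synopsis stop list runs to Day 28 and includes related Grade 4 events. No dose is added for this period. In the first two weeks the same stop list applies, but dosing is not made conditional on it in this way, so the conflict with Table 5 still matters there.

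**The case against.** **The texts differ in force.** Section 5.7 describes Table 5 as guidelines, while Section 6.2 and the synopsis are mandatory. Section 5.7 also states the stop rule for all related Grade 4 events just before introducing the table. An investigator who reads Sections 5.7 and 6 together will conclude that treatment stops. This stands as evidence of intent. It does not correct the two rows or tell someone working from the table which row governs.

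**The restart rows might be meant for unrelated events.** Of the rows at issue, only the last one carries the word related, and Section 5.7 allows but does not require dosing to be maintained for unrelated events. The reading is arguable, but footnote a and the Section 5.7 restriction weigh heavily against it.

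**Safeguards exist.** Laboratory results are reviewed before dosing (Section 7.3.4), immediate safety concerns go to the sponsor (Section 7), serious events are reported within 24 hours (Section 8.2.1.3) and the DSMB receives all adverse event reports (Section 10.5). Section 5.7 also allows deviations after discussion with the sponsor. These lower the risk. A deviation clause still needs a clear default to deviate from.

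**Such events look uncommon at this dose.** Table 7 (25 patients at 20 mg or less) lists no Grade 4 anemia, no Grade 3 or 4 vomiting or diarrhea, and no Grade 4 non-hematologic event. Its only Grade 4 entry is one case of thrombocytopenia. The table is small and shows only terms seen in at least 3 patients with onset by Day 14, so it supports low impact without proving absence.

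**A stronger reading that does not hold.** The continuation criteria for hospitalized patients are written as a AND b OR c. A reader might infer that limb c alone admits a patient with a related Grade 4 event, adding 4 doses (Days 15, 17, 22, 24). The documents do not support this, because continuation also requires that no stopping criterion is met (Step 6).

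**Conclusion.** The point holds in a narrow form. Two rows of Table 5, the general non-hematologic row and life-threatening anemia, contradict five statements that related Grade 4 events end treatment. The vomiting and diarrhea rows share the problem only through their open upper end.

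The intended answer is to stop, and the residual risk is small: at most 3 further doses by Day 14, none after an event on or after the Day 10 dose, and none in Days 15 to 28. This assumes that the event is judged related, that the site follows the specific row and not Section 6.2, and that recovery is immediate. No number of affected patients can be projected from the documents.

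A reader might infer that the platelet and neutrophil rows conflict as well. The documents do not reproduce the CTCAE grade limits, so those rows are not counted. Nor should the point be read as a threat to the trial's conclusions, since it has no effect on power, type I error or the primary analysis. It is worth correcting because it concerns re-exposure after a life-threatening reaction and costs almost nothing to put right.

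**What to change.** Make three changes to Table 5:

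1. Limit the general non-hematologic row to Grade 3.
2. Change the action in the life-threatening anemia row to *Discontinue selinexor*.
3. Add one line: *For any selinexor-related Grade 4 AE, the last row and Section 6.2 override all rows above.*

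The added line also settles the open-ended vomiting and diarrhea rows, and any platelet or neutrophil event that is Grade 4, so those rows need no separate edit.

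The cost is two row edits and one added line in one protocol table, with a memo to sites. Sample size, data collection and analysis do not change.

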## **6. DISCONTINUATION OF STUDY TREATMENT AND PATIENT DISCONTINUATION/WITHDRAWAL**

### **6.1. Discontinuation of Study Treatment**

In rare instances, it may be necessary for a patient to permanently discontinue study treatment. If study treatment is permanently discontinued, the patient will remain in the study to be evaluated for overall mortality. See the SoA for data to be collected at the time of discontinuation of study treatment.

Selinexor should be discontinued for all selinexor-related life-threatening (Grade 4) AEs.

### **6.2. Patient Discontinuation/Withdrawal from the Study**

A patient may withdraw from the study at any time at his/her own request or may be withdrawn at any time at the discretion of the Investigator for safety, behavioral, compliance, or administrative reasons. Waivers for eligibility criteria for enrollment will not be permitted. The criteria given below are reasons the investigator must consider for removal of patients from study.

The Investigator must determine the primary reason for a patient's discontinuation of study treatment/withdrawal from the study and record this information on the electronic case report form (eCRF).

The Investigator may remove a patient from study treatment for any of the following reasons:

- Unacceptable AEs or toxicity that cannot be managed by supportive care
- Significant deviations from inclusion/exclusion criteria
- Missed / unscheduled / off-schedule / incomplete / incorrect assessments that result in patients being put at risk
- Any other medically appropriate reason or significant protocol violation, in the opinion of the Investigator.

The Investigator must remove a patient from study treatment for any of the following reasons:

- Patient withdraws consent to continue study treatment.
- Worsening clinical condition defined as at least 5 days of intubation/ECMO with no evidence of clinical improvement. Patients who are clinically stable based on oxygen requirements on mechanical ventilation will be permitted to remain on study.
- Grade  $\geq 3$  nausea or vomiting despite optimal antiemetic therapy.
- Progression of renal dysfunction requiring dialysis.
- Grade 4 AEs related to selinexor.

### **6.3. Lost to Follow up**

A patient will be considered lost to follow-up if he/she unable to be contacted by the study site.

#### **6.4. Blinding**

The site investigators and patients are blinded to treatment assignment during the conduct of the study. All study staff will be blinded to the treatment assignments and study drug will be administered in a blinded manner.

Unblinding of treatment assignments should be undertaken for safety reasons when it is essential for effective treatment of the patient.

Unblinding is performed using the IRT. When the investigator contacts the IRT to unblind a patient, he/she must provide the requested patient identifying information and confirm the necessity to unblind the patient. The Investigator will then receive details of the drug treatment for the specified patient.

The entire study population will be unblinded at the end of the study and the unblinding information will be shared with each study site.

#### **6.5. Early Termination of the Study**

The study may be terminated at the sole discretion of the Sponsor for any reason, including medical or ethical reasons affecting the continued performance of the study, or difficulties in the recruitment of patients. If this occurs, the Sponsor will notify independent ethics committees (IECs), institutional review boards (IRBs), Investigators, and regulatory authorities.

#### **6.6. End of Study**

End of Study will occur when the last patient has completed the 30-day Safety follow up period (after their last dose of study treatment), has withdrawn consent or has died, whichever comes first.

## **7. STUDY ASSESSMENTS AND PROCEDURES**

- Study procedures and their timing are summarized in the SOA.
- Immediate safety concerns should be discussed with the Sponsor immediately upon occurrence or awareness to determine if the patient should continue or discontinue study treatment.
- Procedures conducted as part of the patient's routine clinical management (e.g., blood count) and obtained prior to signing of the informed consent form (ICF) may be utilized for screening or baseline purposes provided the procedures met the protocol-specified criteria and were performed within the time frame defined in the SOA.
- Please reference the Karyopharm Risk Management Plan for Conduct of Clinical Trials During the COVID-19 Pandemic as the document may address procedures being performed as a part of this clinical trial.

### **7.1. Baseline Assessments**

#### **7.1.1. Demographics**

Patient demographics (including date of birth, sex, ethnicity, and race) will be collected.

#### **7.1.2. Medical History**

The medical history will include co-infections, baseline symptoms as well as active medical conditions. Data from standard-of-care procedures will be part of the patient's medical history and may be used for study purposes.

In addition, the smoking history of the patient will be recorded.

#### **7.1.3. Disease History**

The disease history will include collection of COVID-19 symptom onset date as well as date and time of admission to hospital and reason for admission (COVID-diagnosis/COVID associated complication or Concomitant Illness).

### **7.2. Efficacy Assessments**

Study procedures and their timing are summarized in the SOA.

### **7.3. Safety Assessments**

Planned time points for all safety assessments are provided in the SOA.

#### **7.3.1. Physical Examinations**

The physical examination will be performed according to the standards at each institution.

Complete physical examination, including vital signs, will be performed in the screening visit and if possible, at the End of Study visit. Suspected selinexor associated symptom-directed physical exam should be performed at any time directed by the clinical need as directed by the investigator.

Vital signs will include:

- Body temperature (°C or °F)
- Systolic and diastolic blood pressure and pulse rate
- Respiratory Rate
- Oxygen Saturation
  - If patient requires respiratory assistance, then type of assistance, start and end date as well as reason for removal of mechanical ventilation will be documented in the eCRF.

Clinically relevant findings made after the start of study treatment, which meet the definition of an AE, must be recorded on the AE eCRF.

### **7.3.2. Ordinal Score**

The Ordinal score is a composite measure of clinical improvement and/or survival, assessed on a daily basis.

The severity rating is on a 8-point ordinal scale:

1. Death;
2. Hospitalized, on invasive mechanical ventilation or extracorporeal membrane oxygenation (ECMO);
3. Hospitalized, on non-invasive ventilation or high flow oxygen devices;
4. Hospitalized, requiring supplemental oxygen;
5. Hospitalized, not requiring supplemental oxygen - requiring ongoing medical care (COVID-19 related or otherwise);
6. Hospitalized, not requiring supplemental oxygen - no longer requires ongoing medical care;
7. Not hospitalized, limitation on activities and/or requiring home oxygen;
8. Not hospitalized, no limitations on activities.

### **7.3.3. Electrocardiograms**

Standard 12-lead ECGs will be performed at the time points specified in the SoA.

The Investigator will interpret the ECG using 1 of the following categories: normal, abnormal but not clinically significant, or abnormal and clinically significant.

The time the ECG was performed, and the following parameters will be recorded in the eCRF: heart rate, PR interval, QT interval, QRS interval, and QT corrected using either Bazett's or Fredericia's formula.

### 7.3.4. Clinical Safety Laboratory Assessments

Clinical laboratory tests (detailed in [Table 6](#)) will be performed by the sites' local laboratories. In addition, laboratory tests will be collected and analyzed at times specified on the SoA. More frequent assessments may be performed if clinically indicated.

**Table 6: Clinical Safety Laboratory Tests**

| Hematology      |                                |                      |
|------------------------|--------------------------------|----------------------|
| Hemoglobin             | Leukocytes (with differential) | Neutrophils          |
| Hematocrit             | Platelet count                 | Monocytes            |
| Basophils              | Lymphocytes                    | Eosinophils          |
| Serum Chemistry |                                |                      |
| Sodium                 | Creatinine                     | ALT                  |
| Potassium              | Glucose                        | AST                  |
| Albumin                | Calcium                        | Alkaline phosphatase |
| Bicarbonate            | Phosphate                      | Total bilirubin      |
| BUN/Urea               | LDH                            | Total protein        |
| Coagulation     |                                |                      |
| PT                     | aPTT                           | INR                  |

Blood samples will be analyzed at each study center by a certified laboratory. The Investigator or designee will review the laboratory report after receipt of the results and assess the clinical significance of all abnormal values. Results should be reviewed prior to dosing and appropriate action taken for any clinically significant abnormal values.

At any time during the study, abnormal laboratory values which are clinically relevant (e.g., require dose modification and/or interruption of study treatment, lead to clinical symptoms or signs or require therapeutic intervention), must be documented in the eCRF.

If any abnormal laboratory value or test result constitutes a selinexor related AE, then these must be recorded on the AE eCRF. Values will be documented on the laboratory report until stabilized, or the laboratory value returns to a clinically acceptable range (regardless of relationship to study treatment) or baseline. Any laboratory value that remains abnormal at the End of Study visit that is considered clinically significant will be followed according to accepted medical standards for up to 30 days or until resolution of the abnormality or return to baseline levels. Toxicity will be assessed using the NCI CTCAE, v. 5.0.

Karyopharm must be provided with a copy of the laboratory certification and normal ranges for each parameter measured. In addition, if at any time a patient has laboratory parameters obtained from a different outside laboratory, Karyopharm must be provided with a copy of the certification and normal ranges for that laboratory.

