## 8. ADVERSE EVENTS

### 8.1. Information on Reporting Adverse Events

#### 8.1.1. Definitions

- *Adverse event (AE)*: Any untoward medical occurrence in a patient or clinical investigation subject administered a pharmaceutical product and which does not necessarily have to have a causal relationship with this treatment. An AE can therefore be any unfavorable and unintended sign (including an abnormal laboratory finding, for example), symptom, or disease temporally associated with the use of study treatment, whether or not considered related to the study treatment.
- *Life-threatening adverse event or life-threatening suspected adverse reaction*: An adverse event or suspected adverse reaction is considered "life-threatening" if, in the view of either the investigator or sponsor, its occurrence places the patient or subject at immediate risk of death. It does not include an adverse event or suspected adverse reaction that, had it occurred in a more severe form, might have caused death.
- *Treatment-emergent adverse event (TEAE)*: Any event that was not present prior to the initiation of study treatment or any event already present that worsens in either intensity or frequency following exposure to study treatment.
- *Serious adverse event (SAE)*: Any untoward medical occurrence that, at any dose, results in death; is life threatening (ie, an event in which the patient was at risk of death at the time of the event; it does not refer to an event that hypothetically might have caused death if it were more severe); requires inpatient hospitalization or prolongation of existing hospitalization; results in persistent or significant disability/incapacity; or is a congenital anomaly/birth defect. Important medical events that may not result in death, be life-threatening, or require hospitalization may be considered serious when, based upon appropriate medical judgment, they may jeopardize the patient or subject and may require medical or surgical intervention to prevent one of the outcomes listed in this definition. Examples of such medical events include allergic bronchospasm requiring intensive treatment in an emergency room or at home, blood dyscrasias or convulsions that do not result in inpatient hospitalization, or the development of drug dependency or drug abuse. (See Section 8.2.1.3 for additional information about SAE reporting.)

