### **8.1.2. Recording of Adverse Events**

All AEs that begin or worsen after the patient has provided informed consent will be recorded. Those AEs that occur prior to study dosing, can be captured in the patient's baseline conditions, however if any of these AEs are considered, serious, these are to be reported both to Pharmacovigilance and documented in the eCRF AE log. For events that are considered by the Investigator to be related to the study drug, the monitoring of the AE should be continued through the end of the study, for at least 30 days following last dose of study drug (if the end of the study is within 30 days of the last dose of study drug), or until the AE has resolved.

Investigators should use medical judgment in determining whether a particular symptom or sign is considered to be a part of COVID-19 infection clinical course or not and report them or not as AEs according to such determination. When a clear determination cannot be made by the investigators, a sign or symptom should be reported as AEs. All deaths irrespective of cause of death including due to COVID-19 during the study should be reported to the Sponsor using an SAE form.

Adverse events (including laboratory abnormalities that constitute AEs) should be described using a diagnosis whenever possible, rather than individual underlying signs and symptoms. When a clear diagnosis cannot be identified, each sign or symptom should be recorded as a separate AE.

The Investigator should ask the patient non-leading questions to determine if any AEs have occurred during the study, since the last study visit. Adverse events may also be recorded when they are volunteered by the patient, or through physical examination, laboratory tests, or other clinical assessments.

An AE should be followed until its resolution or until it is judged to be permanent, and assessment should be made at each visit (or more frequently, if necessary) of any changes in severity of the event, the suspected relationship to the study treatment, the interventions required to treat the event, and the outcome.

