#### **8.1.2.1. Laboratory Test Abnormalities**

Laboratory abnormalities that constitute an AE in their own right (i.e., are considered to be clinically significant, induce clinical signs or symptoms, require concomitant therapy, or require changes in study treatment), should be recorded on the Adverse Events eCRF. Whenever

possible, a diagnosis, rather than a symptom should be provided (e.g., anemia instead of low hemoglobin).

Laboratory abnormalities that meet the criteria for an AE should be followed until they have returned to baseline levels (as measured during the Screening visit) or an adequate explanation of the abnormality is identified. When an abnormal laboratory or test result corresponds to a sign/symptom of an already reported AE, it is not necessary to separately record the laboratory/test result as an additional event.

A laboratory abnormality that does not meet the definition of an AE should not be reported as an AE. A Grade 3 or 4 event (considered to be severe per NCI CTCAE, v. 5.0) does not automatically indicate an SAE unless it meets the definition of serious as defined in Section 8.1 and/or as per the opinion of the Investigator. A laboratory abnormality that results in a dose being held or modified would, by definition, be an AE and must be recorded as such in the eCRF.

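### Protocol 7.3.4 names the AE form only for selinexor-related laboratory abnormalities, while 8.1.2 and 8.1.2.1 set no relatedness condition, so all-cause counts of non-serious laboratory TEAEs could be incomplete and vary by site

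*Protocol*

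**What the plan says.** Section 7.3.4 of the protocol, in the text under Table 6, has two steps. Abnormal values that are clinically relevant (the examples are a change to study treatment, resulting symptoms or signs, or a need for intervention) "must be documented in the eCRF"; no particular form is named. The next sentence names the form: "If any abnormal laboratory value or test result constitutes a selinexor related AE, then these must be recorded on the AE eCRF".

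Section 8 states the duty differently. The AE definition in 8.1.1 includes an abnormal laboratory finding and covers events "temporally associated with the use of study treatment, whether or not considered related to the study treatment". Section 8.1.2 says: "All AEs that begin or worsen after the patient has provided informed consent will be recorded". It also asks investigators to judge "whether a particular symptom or sign is considered to be a part of COVID-19 infection clinical course or not and report them or not", and directs that unclear cases be reported. Section 8.1.2.1, the dedicated laboratory rule, sends "Laboratory abnormalities that constitute an AE in their own right" to the Adverse Events eCRF. It treats any abnormality that leads to a held or modified dose as an AE by definition. Neither 8.1.2 nor 8.1.2.1 makes recording depend on relationship to study drug.

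SAP Section 8.1 bases its AE summaries on TEAEs. It lists tables for all TEAEs, TEAEs by causality, Grade 3 or higher TEAEs, and Grade 3 or higher TEAEs by causality. Protocol Section 10.5 promises the DSMB all AE reports, whatever the investigator's causality assessment.

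**The concern.** The SAP tables and the DSMB commitment presuppose that unrelated laboratory AEs are in the AE dataset. If some sites take the qualifier in 7.3.4 as the test for using the AE form, those events are filtered out at entry, and no later analysis of the AE data can restore them.

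This matters because attribution is hard in this trial. Sites are blinded (Section 6.4). Patients have severe COVID-19 and several concomitant treatments. Section 8.1.3 calls an event related when study treatment explains it better than any other drug, intervention or condition. An all-cause comparison between randomised arms does not depend on that individual judgement; a count restricted to events judged related does. Low sodium and low platelets are effects that the protocol itself associates with selinexor (Sections 1.3 and 1.4). With approximately 40 sites planned, mixed readings would also add variation between sites that has nothing to do with patients or treatment.

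**Working it through.** The plan states no figure on this point, so the check is a comparison of texts.

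**The rules side by side**

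| Protocol section | What triggers recording | Where it goes | Relatedness condition |
|---|---|---|---|
| 7.3.1, examination findings | Relevant finding that meets the AE definition | AE form | None |
| 7.3.4, first step | Clinically relevant laboratory value | eCRF, form not named | None |
| 7.3.4, second step | Laboratory value that is a selinexor-related AE | AE form | Yes |
| 7.3.5 | Events that meet the AE or SAE definition; Section 8 cited for detail | Recorded, form not named | None |
| 8.1.2 | Any AE after consent, with judgement on the COVID-19 course | Recorded | None |
| 8.1.2.1 | Laboratory abnormality that is an AE, including any that leads to a held or modified dose | AE form | None |

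**Tracing an event through both rules**

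1. Take a non-serious laboratory abnormality after first dose that is clinically significant or needs treatment, is judged unrelated to study drug, and is not judged part of the COVID-19 course. Under 8.1.2.1 it goes on the AE form and counts as a TEAE. Under 7.3.4 read alone it is documented in the eCRF but need not reach the AE form, so it may not be counted.
2. Change only the relatedness judgement to related. Both sections require the AE form. Treatment-related TEAE counts therefore do not depend on which section a site follows.
3. Change only seriousness. Sections 8.2.1.2 and 8.2.1.3 require every SAE to be recorded and reported whatever its cause. Serious events do not depend on 7.3.4.
4. Suppose instead that the abnormality is judged part of the COVID-19 course. Section 8.1.2 already allows it to be left out, and 8.1.1 counts an abnormal laboratory finding as a sign. Section 7.3.4 does not cause that loss.
5. Suppose the abnormality leads to a dose change. Section 5.7 expects dose modifications to be for selinexor-associated AEs, so most of these would be judged related and fall under step 2.

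**What remains exposed.** The exposed group is non-serious laboratory AEs judged neither drug-related nor part of COVID-19, mainly those that are clinically significant or need treatment without a change of dose. They feed the all-cause, Grade 3 or higher and not-related laboratory counts in SAP 8.1, and the non-serious AE reports to the DSMB.

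**What is protected.** SAP 8.2 summarises laboratory values by visit, worst CTCAE grade and shift from baseline, using laboratory data rather than AE entries. The stopping criteria in Protocol 9.5 use no laboratory AE.

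**The case against.** The strongest reply is that the sections do not conflict. Section 7.3.4 gives a sufficient condition for using the AE form. It does not say that only related events go there, and a site that follows 8.1.2.1 also complies with 7.3.4. Section 7.3.5 comes directly after it and points to Section 8 for detail. Section 9.4.2 even begins by describing the safety evaluation in terms of drug-related AE reports. The named laboratory risks can be compared between arms from the SAP 8.2 tables without any AE form.

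Much of this stands. A reader might infer that 7.3.4 bars unrelated events from the AE form; it does not. A reader might also infer that Section 8 requires recording whatever the cause; that goes too far, because of the COVID-19 judgement in 8.1.2. Nor do the documents support a claim that the SAE tables are at risk.

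The reply does not dispose of the point. The qualifier invites a narrower reading, especially next to a sentence that sends other relevant values to the eCRF in general. The same paragraph of 7.3.4 says that following up a value does not depend on relationship to treatment, so the section does draw that distinction where it wants to. Section 7.3.5 does not say that Section 8 overrides 7.3.4. Section 9.4.2 goes on to list treatment-emergent AEs and related AEs as separate summaries. The SAP 8.2 tables protect the graded laboratory values, not the AE counts.

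**Conclusion.** The two rules are worded inconsistently, and the effect is confined to the outputs identified as exposed above. It rests on one assumption that the documents cannot settle: that some sites treat 7.3.4 as the operative test.

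The size of any bias cannot be derived. A reader might infer that the difference between arms is shrunk by a known amount. One can illustrate this by assuming true incidences of 25% on selinexor and 15% on placebo, with 20% to 50% of events called related in both arms and every site entering related events only. Recorded incidences would be 25% × 0.2 to 0.5 = 5% to 12.5%, and 15% × 0.2 to 0.5 = 3% to 7.5%. The difference would fall from 10 points to 2 to 5. If half the patients in each arm were at such sites, it would be 0.5 × 10 + 0.5 × (2 to 5) = 6 to 7.5 points.

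All these inputs are assumed, and the first case is an extreme one. Unequal attribution changes the picture: with 50% on selinexor and 20% on placebo, the recorded rates are 12.5% and 3%, a difference of 9.5 points, while their ratio rises from 25/15 = 1.67 to 12.5/3 = 4.17. So no general direction of bias is established. Table 7 of the protocol (anaemia 28%, hyponatraemia 24%, thrombocytopenia 16% by Day 14) shows that such events were not rare at low dose. It comes from 25 cancer patients without a control group and says nothing about the size of this effect.

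The inconsistency should be corrected. It is more than clerical, because it bears on what enters the AE dataset, but it does not undermine the safety analysis as a whole.

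**What to change.** In Section 7.3.4, delete the words 'selinexor related' and refer to 8.1.2.1. The sentence would then require any abnormal laboratory value or test result that is an AE under 8.1.2.1 to be entered on the AE form, regardless of relationship to study treatment. The judgement in 8.1.2 about the COVID-19 course stays as it is. Send sites a short reminder with the change.

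The cost is a two-word deletion, a cross-reference with a short clause, and the reminder. Sites will enter somewhat more unrelated laboratory AEs. The change adds no new obligation, because the AE definition, Section 8.1.2.1, the SAP tables and the DSMB commitment already assume this rule. Unrelated events that were not entered before the change may need source review to recover.
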